5.2 Inclusion Criteria

In order to be eligible to participate in this study, an individual must meet all of the following criteria:

1. Subject must be informed of the investigational nature of the study and must be able to sign a written informed consent.
2. Subjects with histologically or cytologically confirmed solid malignancy that has recurred in the head and neck (above the clavicles) region, e.g., subjects with recurrent cutaneous squamous cell carcinoma, salivary gland tumors or esthesioneuroblastoma are eligible for this clinical trial.
3. Subject is 18 years of age or older.
4. Subjects must have undergone previous curative intent therapy, with radiation as a primary or adjuvant therapy.
5. Subjects may have distant metastatic disease, as long as the locoregional site of recurrence is deemed eligible for radiation therapy, and treatment of the loco-regional disease is deemed as taking precedence over treatment of the remaining systemic disease.
6. Subjects must have at least one evaluable (measurable or non-measurable) recurrent lesion that is amenable to radiation therapy.
7. Subjects must demonstrate uptake of CLR 131 via SPECT/CT imaging, as determined by the study radiologist, in the specified site of recurrent/metastatic disease that is to be treated with radiation therapy. There is a subset of up to 6 patients who may continue with CLR 131 treatment without uptake on the SPECT/CT scan after the test dose.
8. Subjects must have an ECOG performance status of 0 – 1.
9. Subjects must have a life expectancy of at least 6 months.
10. The subject has adequate hematologic function, as evidenced by:
 - an absolute neutrophil count (ANC) $\geq 1500 / \mu\text{L}$
 - hemoglobin $\geq 9 \text{ g/dL} (5.58 \text{ mmol/L})$
 - and platelets $\geq 100,000 / \mu\text{L}$
 - If full-dose anticoagulation therapy is used, platelets $\geq 150,000 / \mu\text{L}$ are required.

- If subject is on full-dose anticoagulation therapy, the anticoagulation therapy must be reversible, and reversal of the anticoagulation therapy must not be life-threatening, as judged by the investigator.

11. The subject has adequate renal function as defined by:

- serum creatinine \leq 1.5 times the upper limit of normal (ULN) or Cockcroft-Gault calculated creatinine clearance \geq 60 ml/min

12. The subject has adequate hepatic function as defined by:

- total bilirubin \leq 1.5 mg/dL (25.65 μ mol/L)

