- aspartate transaminase (AST) and alanine transaminase (ALT) \leq 3.0 times the ULN

13. Women of childbearing potential (WOCP) have a confirmed negative urine pregnancy test within 24 hours prior to test dose of CLR 131.

14. Subjects must use a medically acceptable method of birth control such as an oral, implantable, injectable, or transdermal hormonal contraceptive, an intrauterine device (IUD), a double barrier method (condoms, sponge, diaphragm, or vaginal ring with spermicidal jellies or cream), or total abstinence during the study participation and for 6 months after last dose of study drug. Women who are postmenopausal for at least 1 year or surgically sterile (bilateral tubal ligation, bilateral oophorectomy, or hysterectomy) are not considered to be WOCP.

15. Men who are not surgically or medically sterile agree to use an acceptable method of contraception. Male subjects with female sexual partners who are pregnant, possibly pregnant, or who could become pregnant during the study must abstain from intercourse for three weeks after each CLR 131 dose and agree to use condoms at least 6 months after the last dose of study drug. Total abstinence for the same study period is an acceptable alternative.

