7 STUDY SCHEDULE

7.1 Screening

The screening evaluation will occur within 42 days of the test dose of CLR 131. All subjects must provide informed consent prior to any procedures being done specifically for the study and must satisfy the entry criteria. Procedures and data collection at screening are:

- Signed informed consent form (ICF)
- Demographics (birth date, gender, race, ethnicity)
- Medical history, including comprehensive treatment history for underlying malignancy
- Review of concomitant medications
- Physical examination
- Vital signs
- Height, weight
- ECOG performance status
- Complete blood count (CBC) with differential (within 2 weeks prior to test dose to determine eligibility)
- Serum chemistries (within 2 weeks prior to test dose to determine eligibility)
- EKG (within 2 weeks prior to test dose to determine eligibility)
- Urine pregnancy test for WOCP (within 24 hrs prior to the dosimetry test dose)
- Serum thyroid-stimulating hormone (TSH) and free thyroxine (T4)
- Dispense thyroid-protection medication and review instructions with subjects.
Thyroid-protection medication must be taken within 24 hours before CLR 131 dosing and for 14 days after the last CLR 131 dose.
- Adverse event evaluation
- Distribute medication diaries
- Quality of Life surveys
- Saliva and oral swab collection
- Modified barium swallow study
- Oral profile exam
- Diagnostic cross-sectional imaging (any combination of CT, MR, or PET-MR) scans collected from the scans performed as part of standard clinical care.
- Dosimetry Test Dose
- SPECT/CT imaging

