7.2.1.1 Treatment Dose Administration

Subjects who have uptake on SPECT/CT imaging scans are eligible for the treatment portion of the clinical trial. These subjects will be treated and evaluated as follows:

- Vital signs will be collected prior to and 1 hour post CLR 131 infusion
- On day 1 of the treatment period, CLR 131 will be administered through a freely running peripheral IV catheter via a slow infusion of approximately 30 minutes duration. The dose of CLR 131 will be calculated for each subject based on total BSA (not to exceed 2.5 m²) calculated from actual body weight and height at screening.
- SPECT/CT imaging will be performed on days 2, 3, 4-6, and 7-8.
- A second treatment dose of CLR 131 will be given on day 8.
- CBC with differential and serum chemistries weekly for 12 weeks (beginning at day 1 of first treatment dose)

- Confirm subject is taking thyroid protection medication as directed.
- Adverse event evaluation
- Urine pregnancy test for WOCP (within 24 hrs prior to each CLR 131 dose)

7.2.1.2 External beam radiation therapy (EBRT) (approximately 7-14 days after the last CLR 131 treatment dose)

Based on the calculated absorbed dose of CLR 131 to the specific targeted tissue, the subject will undergo standard of care EBRT to complete the designated radiation dose outlined in the re-irradiation plan.

An EKG will be performed on the first day of the SOC EBRT. During the course of EBRT, subjects will be evaluated for any adverse events.

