8.2.1.3 Pregnancy Test

A urine pregnancy test will be completed within 7 days prior to the CLR 131 dosimetry test dose in women of childbearing potential. Women who are postmenopausal for at least 1 year or surgically sterile (bilateral tubal ligation, bilateral oophorectomy, or hysterectomy) are not considered to be of childbearing potential.

Pregnancy testing is being done as part of standard clinical care.

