11.4.4 Reporting of Pregnancy

- Pregnancy will be reported from time of first study drug until 85 days after discontinuation of CLR 131.
- Pregnancy will be reported to UW within 1 business day of discovery of the event.

To ensure subject safety, each pregnancy in a subject on study treatment will be reported to UW within 1 business day of learning of its occurrence. The pregnancy will be followed to determine outcome, including spontaneous or voluntary termination, details of the birth, and the presence or absence of any birth defects, congenital abnormalities, or maternal and/or newborn complications.

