Appendix A: SCHEDULE OF EVENTS

Appendix B: ECOG EASTERN COOPERATIVE ONCOLOGY GROUP PERFORMANCE STATUS

APPENDIX A: SCHEDULE OF EVENTS

Assessment	Screening Period		Treatment Period			Post Treatment					With-drawal ¹⁴
	D-42 to D-1	Dosimetry Test Dose	Treatment dose 1	Treatment dose 2	EBRT	Safety Monitoring Visits ¹²	1 mo post CLR 131 Infusion (± 2 wks)	3 mo post EBRT (± 4 wks)	6 mo post EBRT (± 4 wks)	12 mo post EBRT (± 6 wks)	24 mo post EBRT (± 6 wks) ¹⁷
Informed consent	X										
Demographics	X										
Medical history	X										
Concomitant medication review ¹⁷	X						X	X	X	X	X
Physical exam	X						X	X	X	X	X
Vital signs ¹	X	X ¹⁵	X ¹⁵	X ¹⁵			X	X	X	X	X
Height	X										
Weight	X						X	X	X	X	X
ECOG Performance Status	X						X	X	X	X	X
CBC with diff ²	X ¹¹		X ¹²	X ¹²	X ¹²	X ¹²	X ¹²	X			
Serum chemistries ³	X ¹¹		X ¹²	X ¹²	X ¹²	X ¹²	X ¹²	X			
Pregnancy test for WOCP ⁴		X	X	X							
Electrocardiogram	X ¹⁶				X ¹⁶						
Serum TSH, free T4	X							X	X	X	X
Administration of thyroid-protection	X	X	X	X			X ¹³				

Assessment	Screening Period		Treatment Period			Post Treatment					Withdrawal	
	D-42 to D-1	Dosimetry Test Dose	Treatment dose 1	Treatment dose 2	EBRT	Safety Monitoring Visits ¹²	1 mo post CLR 131 Infusion (± 2 wks)	3 mo post EBRT (± 4 wks)	6 mo post EBRT (± 4 wks)	12 mo post EBRT (± 6 wks)	24 mo post EBRT (± 6 wks) ¹⁷	Withdrawal ¹⁴
medication (start D-1) ⁵												
Adverse event evaluation ⁶	X		X	X	weekly	X	X	X	X	X	X	X
QOL Surveys	X							X	X	X		
Oral swab and saliva collection	X							X	X	X		
Research oral profile exam and SOC Modified barium swallow study	X							X	X			
SPECT/CT Imaging		X ⁷	X ⁸	X								
Disease Assessment												
SOC Diagnostic imaging ⁹	X							X		X	X	
Treatment												
Administration of CLR 131 ¹⁰		X ¹⁵	X ¹⁵	X ¹⁵								
SOC EBRT					X							
Notes												

 1. Vital signs include blood pressure, pulse, respiratory rate, and temperature. 2. CBC to include red blood cell count, hemoglobin, hematocrit, white blood cell count with differential including % neutrophils, lymphocytes, monocytes, eosinophils and basophils, absolute neutrophil count, and platelet count. 3. Serum chemistries to include sodium, potassium, chloride, bicarbonate, BUN, creatinine, glucose, AST, ALT, alkaline phosphatase, total bilirubin, calcium, protein, albumin, and phosphorus. 												

Assessment	Screening Period		Treatment Period			Post Treatment					Withdrawal ¹⁴

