	D-42 to D-1	Dosimetry Test Dose	Treatment dose 1	Treatment dose 2	EBRT	Safety Monitoring Visits ¹²	1 mo post CLR 131 Infusion (± 2 wks)	3 mo post EBRT (± 4 wks)	6 mo post EBRT (± 4 wks)	12 mo post EBRT (± 6 wks)	
4.	A negative urine pregnancy test is required within 24 hours prior to each CLR 131 dose.										
5.	Thyroid protection medication to begin 1 day prior to dosimetry test dose and continue until 14 days post last treatment dose of CLR 131.										
6.	For subjects with unresolved treatment-related toxicity, follow as medically appropriate until resolution or stabilization. AEs will be recorded from time of informed consent until 28 days after last EBRT treatment or 85 days after first treatment dose of CLR 131, whichever is later.										
7.	SPECT/CT imaging will be performed approximately 3 days after CLR 131 dosimetry test dose to confirm tumor uptake. If uptake is not seen at that timepoint, an additional SPECT/CT scan will be performed 7 days post CLR 131 test dose. Uptake in the specified site of recurrent/metastatic disease that is to be treated with radiation therapy will be determined by the study radiologist.										
8.	SPECT/CT imaging will be performed on days 2, 3, 4-6, and 7-8 of the treatment period to visualize and quantitate the biodistribution of CLR 131.										
9.	Imaging may consist of any combination of CT, MR or PET-MR scans as clinically indicated.										
10.	Time between dosimetry test dose and first treatment dose: approximately 14 days, but can be permitted up to 4 weeks. Dosing dates for treatment can be scheduled to start -1 or +3 days to accommodate clinic scheduling (for example: holidays, weekends, treating physician schedules, etc.).										
11.	Screening laboratory tests are to be collected within two weeks of dosimetry test dose to determine eligibility										
12.	CBC with differential and serum chemistries to be done weekly beginning with D1 treatment dose and continue for 12 weeks. Approximately 6 visits will coincide with CLR 131 administration and/or SOC EBRT visits, and ~6 visits may fall outside of SOC EBRT visits.										
13.	Duration of thyroid protection medication: 32-38 days; must take for 14 days post last CLR 131 dose.										
14.	If a subject withdraws or the investigator terminates subject participation prior to the 12 month post EBRT visit, the withdrawal visit procedures will be completed.										

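### Minor: section 8.2.1.3 gives a looser pregnancy-test rule than the rest of the protocol, and section 11.4.4 ends pregnancy reporting at least 96–99 days before the contraception period ends

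*Combined protocol and SAP*

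**What the plan says.** **Pregnancy testing**

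- Section 8.2.1.3, the procedure text for this test: "A urine pregnancy test will be completed within 7 days prior to the CLR 131 dosimetry test dose". It mentions neither treatment dose.
- Section 5.2 opens by stating that "an individual must meet all of the following criteria". Criterion 13 is that women of childbearing potential "have a confirmed negative urine pregnancy test within 24 hours prior to test dose of CLR 131".
- Section 7.1 lists "Urine pregnancy test for WOCP (within 24 hrs prior to the dosimetry test dose"), and section 7.1.1 repeats this among the checks made on the dosing day before infusion.
- Section 7.2.1.1, on the treatment doses, lists "Urine pregnancy test for WOCP (within 24 hrs prior to each CLR 131 dose").
- In the Appendix A schedule, the row "Pregnancy test for WOCP" is marked for the test dose and for both treatment doses. Note 4 reads "A negative urine pregnancy test is required within 24 hours prior to each CLR 131 dose".

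**Pregnancy reporting**

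- Under section 11.4.4, reporting starts with the first study drug and runs "until 85 days after discontinuation of CLR 131". A reported pregnancy is followed to its outcome.
- Criterion 14 requires contraception during study participation and for 6 months after the last dose of study drug. Exclusion criterion 7 excludes anyone expecting to conceive up to 6 months after the last trial treatment.
- Section 11.1.3 counts a congenital anomaly or birth defect as an SAE. For SAEs after the active reporting period, section 11.4.2 asks that those the principal investigator learns of go to the IND holder, and sets related events as the minimum. Section 11.2.2 limits late reporting to SAEs with suspected causality.

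**The concern.** CLR 131 is radioactive, so the pregnancy test before each infusion is a real safety control. Section 8.2.1.3 is where staff would look up how that test is done. Followed alone, it would accept an older test before the test dose and would prompt none before the two treatment doses.

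The second point is a misalignment between two safety periods. The protocol treats conception as a hazard for at least 6 months after the last dose but requires pregnancies to be reported for only 85 days. A pregnancy first identified in the later part of that hazard period may go unreported and unfollowed. Those are outcomes the sponsor of a radiopharmaceutical would want to know.

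**Working it through.** **Testing window.** The documents state no derived figure to reproduce, so the check is a side-by-side comparison.

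| Place | Window | Doses covered |
|---|---|---|
| 8.2.1.3 | 7 days | test dose |
| 5.2, criterion 13 | 24 hours | test dose |
| 7.1 and 7.1.1 | 24 hours | test dose |
| 7.2.1.1 | 24 hours | each CLR 131 dose |
| Appendix A, row and note 4 | 24 hours | all three doses |

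1. Ratio of windows: 7 days × 24 = 168 hours; 168 ÷ 24 = 7. The window in 8.2.1.3 is seven times as long.
2. Doses: 8.2.1.3 names one of the three CLR 131 administrations and leaves out two.
3. Which rule binds: the protocol has no precedence clause. Criterion 13 is a condition of eligibility, and all criteria must be met. A test done within 24 hours also satisfies a 7-day limit, so both instructions can be met only by following the stricter one. The permitted age of the test before the test dose is therefore 24 hours.
4. Treatment doses: criterion 13 covers only the test dose. The other two tests rest on 7.2.1.1 and Appendix A. Section 8.2.1.3 is silent about them and does not waive them.

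**Reporting window.** Inputs: 85 days (11.4.4); 6 months (criterion 14 and exclusion criterion 7). Assumption: discontinuation of CLR 131, which 11.4.4 does not define, means the last dose.

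- Six calendar months last 181 to 184 days, depending on the start date.
- Gap = 6 months − 85 days: 181 − 85 = 96; 184 − 85 = 99.
- Other conventions: 180 − 85 = 95 days; 26 weeks gives 182 − 85 = 97 days.

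This is a minimum, because criterion 14 also covers study participation. If that runs to the visit 24 months after external beam radiation therapy (EBRT), take EBRT starting 7–14 days after the last dose (7.2.1.2), 0 to 35 fractions (at most 70 Gy at 2.0 Gy), an assumed 5 fractions per week (0 to 49 days), and 24 months as 730.5 days:

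- Low: 7 + 0 + 730.5 − 85 = 652.5 days.
- High: 14 + 49 + 730.5 − 85 = 708.5 days.

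**What late-SAE reporting covers.** A late pregnancy with no SAE falls under neither 11.2.2 nor 11.4.2. If there is an SAE, 11.4.2 depends on the principal investigator learning of it, and following a pregnancy to outcome is one way that would happen. Section 11.2.2 then restricts late reports to suspected causality, and the text with Table 2 likewise ties late expedited reports to an attribution of possible or stronger. The backstop is partial, and its own two statements do not agree.

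**The case against.** On testing, the case is that nothing changes in practice. The 24-hour rule appears in five other places. There is one site, and section 16.1 has the coordinator and treating physician sign an eligibility checklist. The Protocol Summary records accrual closed on April 18, 2022 and the last participant's DLT window completed on June 16, 2022, so no CLR 131 dosing appears to remain. This stands, and it is why the point is minor. It does not make 8.2.1.3 correct.

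On reporting, nothing in the documents requires the reporting window to equal the contraception period. The 85-day figure also serves in the general safety window (section 11.2), counted there from the first treatment dose, so it may be a deliberate convention. Section 11.4.4 does not say whether its limit applies to conception or to detection; a pregnancy conceived by day 85 and found later could be read as covered. Unanticipated problems are recorded throughout the study (11.2) and could offer another route. These points stand in part. They make the requirement unclear rather than plainly absent, and the unanticipated-problem route needs all three criteria in 11.1.1 to be met, so it is not assured.

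Three stronger readings are tempting:

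- A reader might infer that women could properly be dosed on a week-old test, or untested at the treatment doses. Criterion 13, 7.2.1.1 and Appendix A rule that out.
- A reader might infer that the 7-day sentence is a leftover from a previous protocol version. The text supplied has no amendment history to show that.
- A reader might infer that late birth defects would necessarily go unreported. They are SAEs, and 11.4.2 asks for late SAEs that come to the investigator's notice.

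**Conclusion.** Both mismatches are in the current text, and both are minor.

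1. Section 8.2.1.3 conflicts with the rest of the protocol: 7 days before one dose, against 24 hours before each of three. The 24-hour rule binds, so the conflict changes little in practice.
2. Pregnancy reporting ends at least 96–99 days before the 6-month contraception and no-conception period does. A pregnancy first identified in between has no clear requirement for a report or for follow-up to outcome. This is a misalignment, not a contradiction.

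The 96–99 days rest on calendar months and on reading discontinuation as the last dose. The number of women of childbearing potential is not given. Whether any participant could still fall in the interval depends on the date of this version, which is not in the text supplied. Neither point touches dose escalation, the DLT rules or any planned analysis.

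**What to change.** - **Section 8.2.1.3:** require a negative urine test no more than 24 hours before every CLR 131 administration, test dose and treatment doses alike, in line with 7.2.1.1 and note 4 of Appendix A. This is a one-line edit; it adds no tests, since they are already scheduled.
- **Section 11.4.4:** run pregnancy reporting to at least 6 months after the last CLR 131 dose. It would help to say whether the limit refers to conception or detection and, if contraception is meant to last for the full 27 months of participation, whether reporting should too. The cost is about 96–99 more days of pregnancy reporting, plus outcome follow-up of any pregnancy found. The visit 3 months after EBRT nominally falls in this interval. With an assumed EBRT course of 1–7 weeks and 3 months taken as 91 days, it comes at 7 + 7 + 91 = 105 to 14 + 49 + 91 = 154 days after the last dose, so participants are already being seen then.

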8.2.1.4 Thyroid Function Tests

Blood will be drawn for serum analysis of TSH and free T4 at screening; 3, 6, and 12 months post EBRT. This is a research procedure for the screening, 3 and 6 month post EBRT visits. This is a standard clinical procedure performed within routine guidelines for the 12 month post EBRT visit.

9 CRITERIA FOR DISEASE ASSESSMENT

For the purposes of this study, subjects will be evaluated for evidence of response and progression at 3 and 12 months post-completion of the EBRT portion of the protocol – see study calendar. Only those subjects who receive a treatment dose of study drug will be assessed for response and/or progression. Those with inadequate uptake after the dosimetry test dose will only be followed for safety measures.

Response and progression will be evaluated in two distinct fashions. For those without evidence of metastatic disease at the time of study enrollment, response and progression will be evaluated using the new international criteria proposed by the Response Evaluation Criteria in Solid Tumors (RECIST) 1.1 Committee (Eisenhauer *et al.*, 2009).

For those with metastatic disease at the time of study enrollment, study lesions will be defined within the locoregional recurrence field that will be receiving EBRT. Those lesions will be assessed for response and progression using RECIST 1.1 criteria. Lesions outside of the radiation field can be assessed for response to CLR 131 alone. Once palliative systemic therapy is initiated for systemic disease burden, subjects will be censored as having disease progression, regardless of the status of the locoregional target lesions.

Note: Lesions are either measurable or non-measurable using the criteria provided below.

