- To evaluate changes in quality of life before and after treatment with CLR 131 in combination with external beam radiation therapy. *Outcome*

measure: Quality of life assessed by MD Anderson Dysphagia Inventory score (MDADI).

- To evaluate salivary flow rate before and after treatment with CLR 131 in combination with external beam radiation therapy. *Outcome measure: stimulated salivary flow.*

Population: Up to twelve adult males and females of all races and ethnic groups with locoregionally recurrent head and neck cancer who may also have distant metastatic disease will be enrolled at the Maximum Tolerated Dose.

Phase: I

Number of Sites: 1, University of Wisconsin Carbone Cancer Center

Description of Intervention: Following informed consent, all subjects will receive a dosimetry test dose of 15 mCi CLR 131 to establish drug uptake by the tumor and enable Monte Carlo dose estimation based on CLR 131 SPECT/CT imaging evaluation.

Subjects who have uptake of the CLR 131 dosimetry test dose at their disease site as determined by the study radiologist will be eligible to participate on the treatment portion of this clinical trial. Subjects showing uptake will receive a cumulative tumor dose of 60-70 Gy using personalized dose calculation of CLR 131 (via Monte Carlo) combined with external beam radiation. In this study, we are also studying a subset of up to 6 patients who do not uptake after the CLR 131 test dose, who will still proceed with treatment with CLR 131.

This clinical trial involves two cohorts of subjects: (a) dose escalation and (b) dose expansion. In the dose escalation phase, an mTPI-2 design, an extension of modified toxicity probability interval (mTPI-2), will be used to identify the maximum tolerated dose (MTD) using cohorts of 4 subjects and up to 3 dose levels of CLR 131. Subjects in the dose escalation phase will receive 2 doses of CLR 131 with the first dose on day 1 followed by the second dose on day 8.

Treatment with CLR 131 on the dose escalation cohort will begin at dose level 1 (15.6 mCi/m²). Subjects at dose level 1 will receive an intravenous infusion of CLR 131 at 15.6 mCi/m² on day 1 followed by a second dose on day 8. Subjects at dose level 2 will receive an intravenous infusion of CLR 131 at 18.75 mCi/m² on day 1 followed by a second dose on day 8.

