4 STUDY DESIGN

This is a Phase 1, single center, dose escalation and dose expansion study of subjects with locoregionally recurrent head and neck cancer who may also have distant metastatic disease. All subjects will receive a dosimetry test dose of CLR 131 (flat dose of 15 mCi) to establish drug uptake by the tumor.

Subjects who have tumor uptake of the CLR 131 dosimetry test dose as determined on SPECT/CT imaging by the study radiologist will be eligible to participate on the treatment portion of this clinical trial. Any subject who demonstrates tumor uptake of CLR 131 by SPECT/CT imaging after the test dose will continue to participate in the treatment portion of the study. Up to six participants who do not demonstrate tumor uptake of CLR 131 by SPECT/CT will also continue with the treatment portion of the study. Based on prior experience of subjects receiving CLR 131, 75 % of eligible subjects are estimated to demonstrate CLR 131 uptake within their tumors.

Subjects showing uptake will receive a cumulative tumor dose of 60-70 Gy using personalized dose calculation of CLR 131 (via Monte Carlo) combined with external beam radiation. If the Monte Carlo dose estimate for any subject is greater than 60 Gy for the 2 doses of CLR 131 (highly unlikely based on preliminary data), then no additional external beam dose will be administered.

All subjects will start thyroid-protection medication the day prior to the CLR 131 dosimetry test dose and will continue to take thyroid protection medication for 14 days after the last CLR 131 dose.

Treatment Plan

Enrollment will start at dose level 1. Subjects will receive 2 doses of CLR 131 intravenously with the first dose on day 1 followed by the second dose on day 8. The dose of CLR 131 will be based on the dose escalation schema.

Dose Escalation Schema	
Dose Level	Doses** of CLR 131
-1*	12.5 mCi/m ²
1	15.6 mCi/m ²
2	18.75 mCi/m ²

*Dose level -1 is the de-escalation dose. The first four patients will be given Dose 1. Dose -1 will only be used if toxicities warrant de-escalation.

** Dose level listed is administered first on day 1 and again on day 8.

SPECT/CT imaging will be performed on days 2, 3, 4-6, and 7-8 of the treatment period to visualize and quantitate the biodistribution of CLR 131. Using the SPECT/CT imaging scans, the [name] lab will perform the Monte Carlo calculations to predict absorbed dose of CLR 131 to tumors and normal structures.

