7.1.1 Dosimetry Test Dose

On the day of dosing, prior to infusion, the following tests and procedures will be done:

- Confirm subject is taking thyroid-protection medication as directed
- Urine pregnancy test for WOCP (within 24 hrs prior to the dosimetry test dose)
- Vital signs will be collected prior to and 1 hour post CLR 131 infusion

CLR 131 will be administered through a freely running peripheral IV catheter via a slow infusion of approximately 30 minutes duration. For the dosimetry test dose, the dose of CLR 131 will be a flat dose of 15 mCi.

- SPECT/CT imaging will be performed approximately three days after infusion to assess tumor uptake of CLR 131. If a subject does not demonstrate CLR 131 uptake on the day 3 SPECT/CT scan, then a repeat SPECT/CT can be performed 7 days after the CLR 131 test dose to reassess for uptake.
- Subjects who demonstrate uptake of CLR 131 on either the day 3 or day 7 SPECT/CT scan, along with up to six patients who do not demonstrate uptake of CLR 131 are eligible for the treatment doses of CLR 131.

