8.1.12 SPECT/CT Imaging

SPECT/CT imaging will be completed at two potential timepoints after the CLR 131 dosimetry test dose to evaluate for tumor uptake: (a) approximately three days and (b) approximately 7 days after the CLR 131 test dose. The SPECT/CT scan on day 7-8 will be completed only if CLR 131 uptake by the tumor is not demonstrated on the day 3 scan. Uptake in the specified site of recurrent/metastatic disease that is to be treated with radiation therapy will be determined by the study radiologist.

Subjects with demonstrated uptake on either SPECT/CT scan (day 3 or day 7) after the test dose and up to six subjects who do not demonstrate uptake of CLR 131 will receive treatment doses of CLR 131. These subjects will have additional SPECT/CT imaging completed in order to visualize and quantitate the biodistribution of the CLR 131 treatment dose. Based on these SPECT/CT imaging scans, the [name] lab will utilize the Monte Carlo method to predict absorbed dose of CLR 131 to tumors and normal structures.

SPECT/CT imaging, which is a research-related procedure, will be performed on days 2, 3, 4-6, and 7-8 following the first CLR 131 treatment dose.

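### Section 9's safety-only sentence makes no exception for treated no-uptake subjects and, followed literally, drops them from response assessment and ORR

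*Combined protocol and SAP*

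**What the plan says.** **Response assessment.** Section 9 gives two rules in consecutive sentences. The first depends on treatment: "Only those subjects who receive a treatment dose of study drug will be assessed for response and/or progression". The second depends on uptake: "Those with inadequate uptake after the dosimetry test dose will only be followed for safety measures".

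**Treatment without uptake.** Five places allow it, up to a cap of six:
- Protocol Summary, Description of Intervention: "a subset of up to 6 patients who do not uptake after the CLR 131 test dose, who will still proceed with treatment"
- Section 4: "Up to six participants who do not demonstrate tumor uptake of CLR 131 by SPECT/CT will also continue with the treatment portion"
- Section 5.2, criterion 7: "subset of up to 6 patients who may continue with CLR 131 treatment without uptake on the SPECT/CT scan after the test dose"
- Section 7.1.1: "along with up to six patients who do not demonstrate uptake of CLR 131 are eligible for the treatment doses of CLR 131"
- Section 8.1.12: "up to six subjects who do not demonstrate uptake of CLR 131 will receive treatment doses of CLR 131"

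Section 7.2.1.1 introduces its list of treatment and evaluation steps without that allowance: "Subjects who have uptake on SPECT/CT imaging scans are eligible for the treatment portion of the clinical trial".

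**Analysis population.** Section 14.2 bases the analysis of outcomes on participants treated at the MTD, up to 12, including escalation subjects treated at that dose. Section 5.5.1 requires, for efficacy, that all CLR 131 doses were received in full and that at least one efficacy assessment followed. Section 3.2.2 defines ORR as a proportion of subjects. None of the three mentions uptake. Section 14.3.2 reports ORR as a proportion with an exact interval and does not state the denominator.

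**The concern.** A treated subject without uptake falls under both Section 9 rules. The first leaves the subject open to response assessment, because a treatment dose was given. The second limits the same subject to safety follow-up, because uptake was inadequate. Both cannot be followed.

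If the second rule prevails, treated subjects leave a named secondary endpoint on the basis of a scan result obtained after enrollment. That result may relate to how much CLR 131 dose the tumor receives, so the exclusion need not be neutral for response. Because Section 14.3.2 does not name the denominator, a team could cite Section 9 to leave these subjects out or Section 14.2 to keep them in, and could choose once responses are known.

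**Working it through.** The plan states no ORR sample size, power or interval width, so there is no figure to reproduce. The check is a comparison of the text, followed by an illustration of size.

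**Step 1: apply each rule to a subject without uptake who received both treatment doses at the MTD and had a follow-up scan.**

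| Place | Condition | Effect on this subject |
|---|---|---|
| Section 14.2 | treated at the MTD | covered, by a general rule |
| Section 9, first rule | received a treatment dose | not excluded |
| Section 5.5.1 | all doses and one efficacy assessment | not excluded |
| Section 3.2.2 | none stated beyond being a subject | not excluded |
| Section 9, second rule | inadequate uptake after the test dose | excluded from response |

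Only Section 14.2 positively covers the subject. The other three set no uptake condition, which is weaker than inclusion. Only the second rule of Section 9 excludes.

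**Step 2: inputs for size.**
- Maximum treated at the MTD: 12 (Section 14.2). All 12 are assumed efficacy-evaluable.
- Expected uptake: 75% (Section 4).
- Number without uptake at the MTD, k: not stated.
- Responders: 4, assumed.
- Interval: exact (Section 14.3.2). The level is not stated; 95% is assumed.

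**Step 3: denominator.** The literal reading leaves 12 − k. If no-uptake subjects are treated as they present, the expected k is 12 × (1 − 0.75) = 3, leaving 9. On the same assumption the chance of at least one is 1 − 0.75^12 = 0.97, and the chance of exactly three is 0.26 (binomial, 12 trials, probability 0.25).

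**Step 4: ORR with k = 3.** The Clopper-Pearson limits for x responders among n are the 2.5% quantile of Beta(x, n − x + 1) and the 97.5% quantile of Beta(x + 1, n − x).

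| Case | All treated | Literal Section 9 |
|---|---|---|
| All 4 responders had uptake | 4/12 = 33% (10–65%) | 4/9 = 44% (14–79%) |
| Equal response rates (3 of 9 and 1 of 3) | 4/12 = 33% (10–65%) | 3/9 = 33% (7–70%) |

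In the first case the estimate rises by 44.4 − 33.3 = 11.1 points. In the second it does not move, and the interval widens from 55 points (65.1 − 9.9) to 63 points (70.1 − 7.5).

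**The case against.** The strongest defense is that the two Section 9 sentences are a pair: the first covers those who are treated, the second those who are not. On that reading there is no conflict. The rest of the protocol supports it. The Protocol Summary says the no-uptake subset is being studied, and Section 7.3 and Appendix A schedule follow-up imaging, quality of life and saliva collection with no uptake condition. This is probably what was meant. It is not what is written, however, and the Protocol Summary and Section 5.2 use nearly the same reference to the test dose for no-uptake subjects who are treated. The defense explains the sentence without repairing it.

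A second defense is that Section 9 sets assessment criteria, not analysis sets, and that Section 14.2 already names the outcome population. This stands in part. A reader might infer that the plan has no defined population for ORR; Section 14.2 shows otherwise. A reader might equally infer that several sections expressly place these subjects in ORR; only Section 14.2 covers them, and it does so without naming them.

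A third defense concerns size. Sections 4 and 7.2.1.2 have external beam radiation complete the designated dose after the CLR 131 contribution is calculated. A tumor with little uptake is therefore not left untreated, and zero response among no-uptake subjects is an extreme assumption. This stands. The 60–70 Gy combined total is stated expressly only for uptake subjects (Protocol Summary, Sections 4 and 6.8), but that does not make zero response likely.

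Finally, Section 7.2.1.1 says uptake subjects are eligible, not that only they are. That is fair. It still omits the allowance in Section 7.1.1, so the wording should be aligned.

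**Conclusion.** The point holds as a sentence that is wrong as written. Taken literally, it removes treated subjects from response assessment and ORR by uptake status, against Section 14.2.

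The likely size is unknown. Under the stated assumptions (12 evaluable at the MTD, three without uptake, four responders, all with uptake), ORR would read 44% instead of 33%. That is an upper illustration for this scenario. With equal response rates only precision is lost, and if no one without uptake was treated at the MTD there is no effect. The Protocol Summary records accrual as closed, so the study team can put in the actual count.

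A reader might infer that the safety conclusions are compromised. The documents do not support this: Section 5.5.1 puts anyone who received any part of a treatment dose in the safety evaluation, and the primary endpoint is adverse events. Nor is a test or threshold at risk, since ORR is secondary and descriptive. The point should be corrected before ORR is reported.

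**What to change.** - **Sections 9 and 7.2.1.1:** reconcile both with Sections 4, 7.1.1 and 8.1.12. This review takes no position on which treatment rule is right.
- **Section 9:** if that is the intent, limit the safety-only sentence to subjects who receive no treatment dose.
- **Section 14.3.2:** state that the ORR denominator is all efficacy-evaluable subjects treated at the MTD, regardless of uptake.

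The cost is one clause, one wording alignment and one sentence. No new data are needed, since follow-up imaging is already scheduled without an uptake condition.
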